## 8.2 Assessment of Response

Assessment of response will begin with the MRI performed just prior to *every odd-numbered* treatment cycle post-surgery. If during any scheduled MRI, the subject has a Complete Response or Partial Response, the MRI should be repeated prior to the next cycle. All scans are to be compared to the smallest measurement scan to date. The subject will then return to the every odd-numbered cycle schedule. This is required to confirm the duration of response. Subjects will be classified as responders if they have a minimum duration of response for 4 weeks at any time after the first post-surgery cycle of lapatinib. MRI scans of subjects showing tumor response will be centrally reviewed by a neuroradiologist who will independently assess tumor size and compute percent tumor regression.

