## **8.0 SAFETY AND QUALITY ASSURANCE**

### **8.1 Criteria for Response Assessment**

Subjects with measurable disease will be assessed by the RANO (radiographic assessment in neuro-oncology) criteria (Wen et al. 2010). For the purposes of this study, subjects should be re-evaluated at the end of every 2 cycles (approximately every 8 weeks) with a contrast-enhanced cranial MRI scan. The response will be determined as outlined in the RANO criteria below.

The MRI obtained prior to starting post-surgery treatment cycles of lapatinib will be used as the baseline MRI for purposes of determining radiographic response.

*Measurable disease.* Bidimensionally, contrast-enhancing, measurable lesions with clearly defined margins by MRI scan, with a minimal diameter of 1 cm, and visible on 2 axial slices which are at least 5 mm apart with 0 mm skip. Measurement of tumor around a cyst or surgical cavity, if necessary, requires a minimum thickness of 3 mm. If there are too many measurable lesions to measure at each evaluation, the investigator must choose the largest two to be followed before a participant is entered on study. The remaining lesions will be considered non-measurable for the purpose of objective response determination. Unless progression is observed, objective response can only be determined when all measurable and non-measurable lesions are assessed.

Complete Response (requires all of the following):

- a) Complete disappearance of all enhancing measurable and non-measurable disease sustained for at least 4 weeks. In the absence of a confirming scan 4 weeks later, this scan will be considered only stable disease.
- b) No new lesions.
- c) All measurable and non-measurable lesions must be assessed using the same techniques as baseline.
- d) Subjects must be off corticosteroids (or on physiologic replacement doses only).
- e) Stable or improved non-enhancing (T2/FLAIR) lesions.
- f) Stable or improved clinically.

**Note:** Subjects with non-measurable disease cannot have a complete response. The best response possible is stable disease.

Partial Response (requires all of the following):

- a) Greater than or equal to 50% decrease compared to baseline in the sum of products of perpendicular diameters of all measurable enhancing lesions sustained for at least 4 weeks. In the absence of a confirming scan 4 weeks later, this scan will be considered only stable disease.
- b) No progression of non-measurable disease.
- c) No new lesions.

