- d) All measurable and non-measurable lesions must be assessed using the same techniques as baseline.
- e) The corticosteroid dose at the time of the scan evaluation should be no greater than the dose at time of baseline scan.
- f) Stable or improved non-enhancing (T2/FLAIR) lesions on same or lower dose of corticosteroids compared to baseline scan.
- g) Stable or improved clinically.

**Note:** Subjects with non-measurable disease cannot have a partial response. The best response possible is stable disease.

Stable Disease (requires all of the following):

- a) Does not qualify for CR, PR, or progression.
- b) The designation of stable disease requires a minimum of 4-week duration.
- c) All measurable and non-measurable sites must be assessed using the same techniques as baseline.
- d) Stable non-enhancing (T2/FLAIR) lesions on same or lower dose of corticosteroids compared to baseline scan. In the event that the corticosteroid dose was increased for new symptoms and signs without confirmation of disease progression on neuroimaging, and subsequent follow-up imaging shows that this increase in corticosteroids was required because of disease progression, the last scan considered to show stable disease will be the scan obtained when the corticosteroid dose was equivalent to the baseline dose.

e) Stable clinically.

Progressive Disease (defined by any of the following):

- a)  $\geq 25\%$  increase in sum of the products of perpendicular diameters of enhancing lesions compared to the smallest tumor measurement obtained either at baseline (if no decrease) or best response, on stable or increasing doses of corticosteroids.\*
- b) Significant increase in T2/FLAIR non-enhancing lesion on stable or increasing doses of corticosteroids compared to baseline scan or best response following initiation of therapy,\* not due to co-morbid events (radiation therapy, demyelination, ischemic injury, infection, seizures, postoperative changes, or other treatment effects).
- c) Any new lesion.
- d) Clear clinical deterioration not attributable to other causes apart from the tumor (e.g., seizures, medication adverse effects, complications of therapy, cerebrovascular events, infection, etc.) or changes in corticosteroid dose. The definition of clinical deterioration is left to the discretion of the treating physician, but it is recommended that a decrease in 20% of KPS or from any baseline to 50% or less be considered, unless attributable to comorbid events.

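### Section 8.2 sets the smallest scan to date as the reference for all scans, while 8.1 defines partial response against the pre-Cycle 1 baseline MRI; if 8.2 is applied to response, ORR could be understated

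*Combined protocol and SAP*

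**What the plan says.** Section 8.1 (Criteria for Response Assessment) sets out the response categories and says of them: "The response will be determined as outlined in the RANO criteria below". It fixes the baseline: "The MRI obtained prior to starting post-surgery treatment cycles of lapatinib will be used as the baseline MRI for purposes of determining radiographic response". The size criterion for PR is "Greater than or equal to 50% decrease compared to baseline in the sum of products of perpendicular diameters of all measurable enhancing lesions", held for at least 4 weeks. For a scan that meets the criterion but is not followed up, it adds: "In the absence of a confirming scan 4 weeks later, this scan will be considered only stable disease". Progression has a different reference: the 25% increase is "compared to the smallest tumor measurement obtained either at baseline (if no decrease) or best response, on stable or increasing doses of corticosteroids".

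Section 8.2 (Assessment of Response) has the MRI repeated before the next cycle when a CR or PR is seen. It then says: "All scans are to be compared to the smallest measurement scan to date". The patient next returns to the odd-cycle schedule, and the section explains that the repeat is needed to confirm how long the response lasts. Sections 8.2 and 8.4 have a central neuroradiologist compute percent regression for scans that show a response. Neither names the scan from which regression is measured.

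Section 11 (Secondary and Exploratory Objectives, item 4) estimates ORR as the proportion with PR or CR, with an exact binomial 95% confidence interval. Item 6 defines progression for PFS as an increase of at least 25% from the baseline scan, with a confirmatory scan at least 8 weeks later.

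**The concern.** The baseline and the smallest scan to date stop being the same scan as soon as a tumour shrinks, which is exactly when response is being judged. The 8.2 sentence is worded for all scans, stands under a heading about response, and directly follows the instruction to repeat the MRI after a CR or PR. A reader could reasonably apply it to that repeat scan. The smallest earlier scan is then usually the one that first showed the response, and the confirmatory scan would have to fall by half again.

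ORR is a stated objective, which section 11 presents as evidence of biological activity, and an unconfirmed response is downgraded to stable disease. The possible error runs in one direction only, towards too few responses. Central review would not reliably catch it: the reader has no stated denominator, and a response missed at the site is not among the scans sent for review.

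**Working it through.** The documents give no expected ORR, and no sample size or error rate depends on it, so there is no planned figure to reproduce. The check applies the thresholds in 8.1 to the same scan series under each reference.

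**Inputs.** The PR threshold is a fall of at least 50%, confirmed 4 weeks later (8.1). The progression threshold is a rise of at least 25% from the smallest measurement (8.1). The candidate references are the pre-Cycle 1 baseline (8.1) and the smallest scan to date (8.2). The tumour products below are assumptions for illustration.

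**Formulas.** With S0 the baseline product and Si the product at scan i:
- change from baseline = (Si - S0) / S0
- change from smallest = (Si - min(S0, ..., Si-1)) / min(S0, ..., Si-1)

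**Results.**

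| Series | Change from baseline | Reading under 8.1 | Change from smallest earlier scan | Reading if 8.2 is applied to PR |
|---|---|---|---|---|
| Gradual: 1000, 700, 450, 450 | -30%, -55%, -55% | confirmed PR | -30%, -35.7%, 0% | never PR |
| Abrupt, then stable: 100, 45, 45 | -55%, -55% | confirmed PR | -55%, 0% | PR not confirmed |
| Abrupt, slight regrowth: 100, 40, 48 | -60%, -52% | confirmed PR | -60%, +20% | PR not confirmed; not progression |
| Abrupt, halving again: 100, 45, 22 | -55%, -78% | confirmed PR | -55%, -51.1% | confirmed PR |

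For the gradual series: (450 - 1000)/1000 = -55%, but (450 - 700)/700 = -35.7% and (450 - 450)/450 = 0%.

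**General condition.** If 8.2 is applied to PR, the first qualifying scan needs S1 ≤ 0.5 × S0 and the confirmatory scan needs S2 ≤ 0.5 × S1. So S2 ≤ 0.25 × S0: confirmation would require a fall of at least 75% from baseline, where 8.1 asks for 50%. A response that deepens is safe only if it halves again.

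**Effect on ORR.** The denominator at analysis is not known in advance. As an assumption, take the 33 planned patients (18 in Group A plus 15 in the Reference Group) and, as a lower case, 18. One lost responder changes the estimate and its exact 95% interval as follows:
- n = 33: from 1/33 = 3.0% (0.1% to 15.8%) to 0/33 = 0% (0% to 10.6%)
- n = 18: from 1/18 = 5.6% (0.1% to 27.3%) to 0/18 = 0% (0% to 18.5%)

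These figures show what a single misclassification would do. They do not predict how many would occur.

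**The case against.** The strongest reply is that 8.1 already settles the matter. It says that its own criteria determine response, names the baseline MRI for that purpose, and defines PR against it. Section 8.2 uses PR as a term already defined, gives no threshold of its own, and does not say that it replaces 8.1. A demand for a second 50% fall therefore combines the threshold in 8.1 with the reference in 8.2, a rule written nowhere. A compatible reading also exists: every scan must be compared with the smallest in order to apply the progression rule, and nothing in 8.2 excludes a baseline comparison as well.

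Most of this stands. A reader might infer that the plan, as written, makes gradual or stable partial responses uncountable, or that 8.2 contradicts 8.1 throughout. The documents support neither inference. The smallest scan is the correct reference for progression under 8.1; CR means disappearance of enhancing disease and does not turn on the reference; and the harm arises only if someone lets 8.2 override the PR definition.

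The reply does not remove the ambiguity. No order of precedence between the two sections is stated, the 8.2 sentence covers all scans in the very place where confirmation is described, and the central reader is given no other reference. Nor do other sections show the intended rule: section 11 measures progression for PFS from baseline, and section 10.1 gives a 25% increase without naming a reference.

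**Conclusion.** The point holds as a wording conflict with a conditional effect. Section 8.2 gives one reference for all scans, whereas 8.1 requires baseline for PR and the smallest measurement for progression. If 8.2 is applied to response at a site or at central review, gradual partial responses, and those that hold or regrow slightly by the confirmatory scan, could be recorded as stable disease and ORR would be too low. How often that would happen cannot be estimated from the documents. With 18 to 33 patients, each lost responder lowers ORR by 5.6 to 3.0 percentage points.

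The endpoint is secondary/exploratory and only estimated; no decision rule uses it. CR, responses that halve again by confirmation, the primary PK and PD endpoints and the sample size are unaffected. The priority is low, but the correction costs almost nothing.

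**What to change.** Amend the sentence in 8.2 to say that PR and its confirmation are judged against the pre-Cycle 1 baseline MRI, as 8.1 already states, and that comparison with the smallest measurement to date is for progression only. State in 8.2 and 8.4 that the central reader computes percent regression from the same baseline MRI.

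The progression half should not be added in isolation. Section 8.1 uses the smallest measurement, section 11 item 6 uses the baseline scan, and section 10.1 names no reference. These passages need to be reconciled, or section 11 should say that its PFS definition differs on purpose.

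The cost is one sentence in 8.2, a clause for the central reader and a cross-check of sections 10.1 and 11. No visits, scans or patients are added. The change should be made before any response is adjudicated.

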## 8.3 Safety assessments

Safety assessments will consist of monitoring and recording all adverse events and serious adverse events, the regular monitoring of hematology, blood chemistry and urine values, regular measurement of vital signs, and the performance of physical/neurological examinations, and ECGs.

## 8.4 Quality Assurance

**Neuropathology:** The neuropathologic diagnosis of (study disease) will be made at the respective institution. If any question arises regarding the accuracy of the neuropathologic diagnosis, slides (and pathological blocks, if necessary) will be reviewed by the central review pathologist. For protocols with “response” as an outcome, all patients with a documented complete response or partial response will have representative pathology slides undergo central review.

**Neuroradiology:** MRI scans of patients showing tumor response will be centrally reviewed by a neuroradiologist who will independently assess tumor size and compute percent tumor regression.

**Neuro-oncology:** The local investigator at the participating institution will communicate to the ABTC Central Office any unexpected neurological effects such as change in seizure frequency, alteration in neuromuscular function, alteration in cognitive function, or fluctuations in serum anticonvulsant drug levels.

**Adherence to protocol therapy:** As a quality assurance measure for the treatment delivered on this protocol, primary patient records may be reviewed. The records to be examined will be selected retrospectively and at random; complete records must therefore be maintained on each patient treated on the protocol. These records should include primary documentation (e.g., laboratory report slips, X-ray reports, scan reports, pathology reports, physician notes, etc.), which confirm that:

- The patient met each eligibility criterion.
- Signed informed consent was obtained prior to treatment.
- Treatment was given according to protocol (dated notes about doses given; any reasons for any dose modifications).
- Toxicity was assessed according to protocol (laboratory report slips, etc.).
- Response was assessed according to protocol (MRI scan, lab reports, dated notes on measurements and clinical assessment, as appropriate).
- NCI Drug Accountability Records were maintained for this protocol.

## 9.0 MONITORING OF PATIENTS

### 9.1 Tables of Required Observations

#### Group A

	Baseline	Pre-Surgery	Day of Surgery	Post-Surgery	Post-Surgery Cycles	Pre-Odd Cycles	Pre-Even Cycles	Every 3 Cycles	Off Treatment (within 7 days)	30-Day Follow-Up
Lapatinib		6			6					
Adverse Event Evaluations			7	10		17	17		12	13
Glucocorticoids Dose	1			19		17			12	
MRI	1			19		17,18			12	
H&P/Neuro exam	1					17	17		12	
KPS	1					17	17		12	
Vital Signs	1,2					2,17	2,17		2,12	
CBC, platelets, Differential	1		11			17	17		12	
Serum Chemistry	1,3		3,14			3,17	3,17		3, 12	
APTT or PTT	1									
Serum Pregnancy Test	1,4									
Echocardiogram	1					16		16		
12-Lead Electrocardiogram	15									
Plasma Pharmacokinetics	8		8							
Fresh Tumor Tissue			9							
Archived Tumor Tissue	5									

- 1 – All baseline measurements must be done within 21 calendar days prior to start of treatment, unless otherwise indicated.
- 2 – Including blood pressure, respiratory rate, heart rate, temperature, weight, and height: height is required at baseline only.
- 3 – Albumin, alkaline phosphatase, total bilirubin, calcium, creatinine, magnesium, phosphorus, potassium, SGOT, SGPT, sodium.
- 4 – Females with child-bearing potential must have a negative serum pregnancy test.
- 5 – Archived tumor tissue from initial surgery at diagnosis of high-grade glioma. See Section [9.5.2](#)
- 6 – Four doses of lapatinib will be administered pre-operatively starting 2 days prior to the day of surgery with the last pre-operative dose taken 3-5 hours prior to scheduled surgery: see Section [4.1](#) for schedule. One additional dose is permitted if unexpected logistical problems delay surgery.  
Post-operatively patients will receive lapatinib twice a day for two consecutive days every 7 days (2 days on/5 days off) in 28-day cycles. Patients are required to keep a pill diary. See Section [4.3.1](#).
- 7 – Patient should be seen on the day of surgery (prior to the the time of surgery) to evaluate for AEs.
- 8 – Plasma specimens for pharmacokinetics will be obtained at baseline and pre- and post-surgical resection. See Section [9.5.3](#) for details.
- 9 – Fresh tumor tissue for correlative studies will be collected day of surgery. See Section [9.5.1](#), [9.5.2](#), and [9.5.4](#) for details.
- 10 – Within 3 days post-surgery.
- 11 – Within minus 1 day
- 12 – Evaluations done within +7 days of off-treatment date unless indicated; do not repeat: if MRI within 14 days of off-treatment date; if H&P /neuro-exam, KPS, labs within minus 5 days of off-treatment date.
- 13 – Adverse Events must be followed for at least 30 days from the last dose of lapatinib, until resolution, within +14 days.

Drug Distribution and Pharmacodynamic Study of Pulsatile Lapatinib in Surgically Accessible EGFR-Amplified Recurrent High-Grade Glioma

ABTC # 1302

NCI # ABTC-1302

PI: [name]

- 14 – After last dose of study drug, prior to surgery
- 15 – 12-lead electrocardiogram (ECG) must be performed within 2 weeks prior to start of treatment, with QTc  $\leq$ 470 msec.
- 16 – LVEF must be monitored every 12 weeks (3 cycles), including pre-Cycle 1, to ensure that LVEF does not decline below the institutional lower limit of normal. See Section [5.2.2](#).
- 17 – Within minus 5 calendar days of starting cycle
- 18 – For Cycle 1 only, perform scan only if patient will start cycle  $>$ 21 days from post-operative scan (patient must have scan within  $\leq$ 21 days of Cycle 1 start). Record glucocorticoid dose at time of MRI.
- 19 – Perform MRI 1-3 days post-operatively. Record glucocorticoid dose at time of MRI

### Reference Group

	Baseline	Day of Surgery	Post-Surgery	Post-Surgery Cycles	Pre-Odd Cycles	Pre-Even Cycles	Every 3 Cycles	Off Treatment (within 7 days)	30-Day Follow-Up
Lapatinib				9					
Adverse Event Evaluations			7		10	10		12	13
Glucocorticoids Dose	1		8		10			12	
MRI	1		8		10,14			12	
H&P/Neuro exam	1				10	10		12	
KPS	1				10	10		12	
Vital Signs	1,2				2,10	2,10		2,12	
CBC, platelets, Differential	1				10	10		12	
Serum Chemistry	1,3				3,10	3,10		3,12	
APTT or PTT	1								
Serum Pregnancy Test	1,4								
Echocardiogram	1				11		11		
12-Lead Electrocardiogram	15								
Fresh Tumor Tissue		6							
Archived Tumor Tissue	5								

- 1 – All baseline measurements must be done within 21 calendar days prior to start of treatment, unless otherwise indicated.
- 2 – Including blood pressure, respiratory rate, heart rate, temperature, weight, and height: height is required at baseline only.
- 3 – Albumin, alkaline phosphatase, total bilirubin, calcium, creatinine, magnesium, phosphorus, potassium, SGOT, SGPT, sodium.
- 4 – Females with child-bearing potential must have a negative serum pregnancy test.
- 5 – Archived tumor tissue from initial surgery at diagnosis of high-grade glioma. See Section [9.5.2](#)
- 6 – Fresh tumor tissue for correlative studies will be collected day of surgery. See Section [9.5.1](#), [9.5.2](#), and [9.5.4](#) for details.
- 7 – Within 3 days post-surgery.
- 8 – Perform MRI 1-3 days post-operatively. Record glucocorticoid dose at time of MRI.
- 9 – Post-operatively patients will receive lapatinib twice a day for two consecutive days every 7 days (2 days on/5 days off) in 28-day cycles. Patients are required to keep a pill diary. See Section [4.3.1](#).
- 10 – Within minus 5 calendar days of starting cycle
- 11 – LVEF must be monitored every 12 weeks (3 cycles), including pre-Cycle 1, to ensure that LVEF does not decline below the institutional lower limit of normal. See Section [5.2.2](#).
- 12 – Evaluations done within +7 days of off-treatment date unless indicated; do not repeat: if MRI within 14 days of off-treatment date; if H&P /neuro-exam, KPS, labs within minus 5 days of off-treatment date.
- 13 – Adverse Events must be followed for at least 30 days from the last dose of lapatinib, until resolution, within +14 days.
- 14 – For Cycle 1 only, perform scan only if patient will start cycle >21 days from post-operative scan (patient must have scan within ≤21 days of Cycle 1 start). Record glucocorticoid dose at time of MRI.
- 15 – 12-lead electrocardiogram (ECG) must be performed within 2 weeks prior to start of treatment, with QTc ≤470 msec.

## 9.2 Adverse Events

Patients will be evaluated for toxicity if they have received at least one dose of lapatinib.

The timely reporting of adverse events (including toxic deaths) is required by the Food and Drug Administration. The reporting of toxicities is part of the data reporting for this study.

The following Adverse Events must be reported to the ABTC Central Office and the NCI in the manner described in addition to the Institution's Institutional Review Board.

All adverse events will be mailed/emailed to the ABTC Central Office by the investigative site in a timely manner. See Section [12.0](#) – Records to be Kept.

All CTEP/NCI Adverse Drug Reactions will be reported to the ABTC Central Office and CTEP/NCI within 24 hours of known event (unless otherwise specified).

### 9.2.1 Comprehensive Adverse Events and Potential Risks list (CAEPR) For Lapatinib (GW572016, NSC 727989)

The Comprehensive Adverse Event and Potential Risks list (CAEPR) provides a single list of reported and/or potential adverse events (AE) associated with an agent using a uniform presentation of events by body system. In addition to the comprehensive list, a subset, the Specific Protocol Exceptions to Expedited Reporting (SPEER), appears in a separate column and is identified with bold and italicized text. This subset of AEs (SPEER) is a list of events that are protocol specific exceptions to expedited reporting to NCI (except as noted below). Refer to the 'CTEP, NCI Guidelines: Adverse Event Reporting Requirements'

[http://ctep.cancer.gov/protocolDevelopment/electronic\\_applications/docs/aeguidelines.pdf](http://ctep.cancer.gov/protocolDevelopment/electronic_applications/docs/aeguidelines.pdf) for further clarification. *Frequency is provided based on 6120 patients.* Below is the CAEPR for Lapatinib (GW572016).

**NOTE:** Report AEs on the SPEER **ONLY IF** they exceed the grade noted in parentheses next to the AE in the SPEER. If this CAEPR is part of a combination protocol using multiple investigational agents and has an AE listed on different SPEERs, use the lower of the grades to determine if expedited reporting is required.

Version 2.8, February 4, 2019

Adverse Events with Possible Relationship to Lapatinib (GW572016) (CTCAE 5.0 Term) [n= 6120]			Specific Protocol Exceptions to Expedited Reporting (SPEER)
Likely (>20%)	Less Likely (<=20%)	Rare but Serious (<3%)	
BLOOD AND LYMPHATIC SYSTEM DISORDERS			
	Anemia		
CARDIAC DISORDERS			
		Left ventricular systolic dysfunction	Left ventricular systolic dysfunction (Gr 2)
GASTROINTESTINAL DISORDERS			
	Abdominal distension		Abdominal distension (Gr 2)
	Abdominal pain		Abdominal pain (Gr 2)
	Anal mucositis		Anal mucositis (Gr 2)
Diarrhea			Diarrhea (Gr 3)
	Dyspepsia		Dyspepsia (Gr 2)
	Flatulence		Flatulence (Gr 2)
	Mucositis oral		Mucositis oral (Gr 2)
	Nausea		Nausea (Gr 2)
	Rectal mucositis		Rectal mucositis (Gr 2)
	Small intestinal mucositis		Small intestinal mucositis (Gr 2)
	Vomiting		Vomiting (Gr 2)
GENERAL DISORDERS AND ADMINISTRATION SITE CONDITIONS			
	Fatigue		Fatigue (Gr 2)
	Flu like symptoms		Flu like symptoms (Gr 2)
HEPATOBIILIARY DISORDERS			
		Hepatic failure	Hepatic failure (Gr 2)
IMMUNE SYSTEM DISORDERS			
		Allergic reaction	
INFECTIONS AND INFESTATIONS			
	Infection 		
INVESTIGATIONS			
	Alanine aminotransferase increased		Alanine aminotransferase increased (Gr 2)
	Aspartate aminotransferase increased		Aspartate aminotransferase increased (Gr 3)
	Blood bilirubin increased		Blood bilirubin increased (Gr 2)
		Ejection fraction decreased	
		Electrocardiogram QT corrected interval prolonged	Electrocardiogram QT corrected interval prolonged (Gr 2)
	Neutrophil count decreased		
METABOLISM AND NUTRITION DISORDERS			
	Anorexia		Anorexia (Gr 2)
	Dehydration		Dehydration (Gr 2)
MUSCULOSKELETAL AND CONNECTIVE TISSUE DISORDERS			
	Arthralgia		
	Myalgia		
NERVOUS SYSTEM DISORDERS			
	Dysgeusia		Dysgeusia (Gr 2)

Adverse Events with Possible Relationship to Lapatinib (GW572016) (CTCAE 5.0 Term) [n= 6120]			Specific Protocol Exceptions to Expedited Reporting (SPEER)
Likely (>20%)	Less Likely (<=20%)	Rare but Serious (<3%)	
	Headache		Headache (Gr 2)
RESPIRATORY, THORACIC AND MEDIASTINAL DISORDERS			
	Cough		
	Epistaxis		
	Laryngeal mucositis		Laryngeal mucositis (Gr 2)
	Pharyngeal mucositis		Pharyngeal mucositis (Gr 2)
		Pneumonitis	
	Tracheal mucositis		Tracheal mucositis (Gr 2)
SKIN AND SUBCUTANEOUS TISSUE DISORDERS			
	Alopecia		
	Dry skin		
		Erythema multiforme	
	Nail changes		
		Palmar-plantar erythrodysesthesia syndrome	
	Pruritus		Pruritus (Gr 2)
	Rash acneiform		Rash acneiform (Gr 2)
Rash maculo-papular			Rash maculo-papular (Gr 2)
		Stevens-Johnson syndrome	
		Toxic epidermal necrolysis	
VASCULAR DISORDERS			
	Flushing		Flushing (Gr 2)
	Hot flashes		

This table will be updated as the toxicity profile of the agent is revised. Updates will be distributed to all Principal Investigators at the time of revision. The current version can be obtained by contacting [[contact]](mailto:[contact]). Your name, the name of the investigator, the protocol and the agent should be included in the e-mail

Infection includes all 75 sites of infection under the INFECTIONS AND INFESTATIONS SOC.

**Adverse events reported on lapatinib (GW572016) trials, but for which there is insufficient evidence to suggest that there was a reasonable possibility that lapatinib (GW572016) caused the adverse event:**

**BLOOD AND LYMPHATIC SYSTEM DISORDERS** - Febrile neutropenia

**CARDIAC DISORDERS** - Atrial fibrillation; Chest pain - cardiac; Pericarditis; Sinus tachycardia

**EYE DISORDERS** - Blurred vision

**GASTROINTESTINAL DISORDERS** - Ascites; Constipation; Dysphagia; Gastritis; Hemorrhoids; Ileus; Pancreatitis

**GENERAL DISORDERS AND ADMINISTRATION SITE CONDITIONS** - Edema limbs; Fever; Non-cardiac chest pain; Pain

**IMMUNE SYSTEM DISORDERS** - Anaphylaxis

**INVESTIGATIONS** - Alkaline phosphatase increased; Creatinine increased; GGT increased; INR increased; Lymphocyte count decreased; Platelet count decreased; Weight loss; White blood cell decreased

**METABOLISM AND NUTRITION DISORDERS** - Hyperglycemia; Hyperphosphatemia; Hypoalbuminemia; Hypoglycemia; Hypokalemia; Hyponatremia; Hypophosphatemia

**MUSCULOSKELETAL AND CONNECTIVE TISSUE DISORDERS** - Back pain; Bone pain; Flank pain

**NEOPLASMS BENIGN, MALIGNANT AND UNSPECIFIED (INCL CYSTS AND POLYPS)** - Tumor hemorrhage

**NERVOUS SYSTEM DISORDERS** - Cerebrospinal fluid leakage; Depressed level of consciousness; Dizziness; Intracranial hemorrhage; Nervous system disorders - Other (altered dream pattern); Nervous system disorders - Other (sleep walking); Paresthesia; Peripheral motor neuropathy; Peripheral sensory neuropathy; Syncope

**PREGNANCY, PUERPERIUM AND PERINATAL CONDITIONS** - Pregnancy loss

**PSYCHIATRIC DISORDERS** - Insomnia

**RENAL AND URINARY DISORDERS** - Acute kidney injury

**RESPIRATORY, THORACIC AND MEDIASTINAL DISORDERS** - Dyspnea; Hypoxia; Oropharyngeal pain; Pleural effusion; Pulmonary edema; Pulmonary fibrosis

**SKIN AND SUBCUTANEOUS TISSUE DISORDERS** - Nail loss; Pain of skin; Skin and subcutaneous tissue disorders - Other (onychocryptosis); Skin and subcutaneous tissue disorders - Other (seborrheic dermatitis); Skin ulceration; Urticaria

**VASCULAR DISORDERS** - Hematoma; Hypertension; Hypotension; Thromboembolic event; Vascular disorders - Other (hypovolemia)

**Note:** Lapatinib (GW572016) in combination with other agents could cause an exacerbation of any adverse event currently known to be caused by the other agent, or the combination may result in events never previously associated with either agent.

